Most MRSA infections among HIV-infected patients involve the soft-tissues and present as folliculitis, furuncles, carbuncles, abscesses, cellulitis, or necrotizing fasciitis [7]. HIV-infected persons presenting with a history of a “bug bite” or soft tissue infection should be evaluated for MRSA. Treatment of MRSA infections has not been standardized and the optimal therapeutic regimen remains unknown. Of note, antibiotic resistance for community-acquired strains is typically less than for nosocomial isolates due to reduced antibiotic pressures and due to the smaller chromosomal cassette. However, increasing resistance to antibiotics has been noted among community-acquired isolates, including rising rates of clindamycin resistance [28, 29].

Whether HIV patients should be screened routinely for MRSA carriage and whether decolonization procedures, with hexachlorophene (pHisoHex®) soaps and nasal mupirocin (Bactroban®), should be instituted remains unknown as there are no formal guidelines addressing these questions. Regarding screening for MRSA carriage, studies among HIV patients have suggested that high risk sexual activities and potentially perirectal carriage of MRSA may be important in the epidemiology of CA-MRSA infections. Although, a recent study showed limited use of perianal cultures for MRSA screening, this study was solely among patients at a rehabilitation unit [30a], rather than HIV patients who likely have divergent risk factors and routes of MRSA transmission. A recently presented abstract in HIV patients showed a poor correlation between MRSA nares carriage and MRSA infection [30b], hence we will evaluate the possible additive benefit of perianal and throat cultures in this cohort. Our study will examine nares, throat, axilla, groin, and perirectal surveillance cultures for MRSA among HIV patients.

Although there are no formal recommendations for the use of TMP/SMX to prevent MRSA infections among HIV-infected patients, those patients requiring this antibiotic for other indications (e.g., *Pneumocystis carinii* pneumonia or *Toxoplasma* prophylaxis) have lower rates of MRSA infection. Given the higher rates of community-acquired MRSA among HIV-infected patients and that this group may have a propensity towards recurrent infections [5], formulating preventive strategies would be useful.

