Patients who are colonized with MRSA and who reside locally to the medical treatment facility and are able to return to the clinic will have repeat swabs (five swabs from sites listed above) every month (+/- 7 days). A month will be specifically defined as 28 days. Those who have repeat positive colonization swabs during this initial 6 month follow-up period will be observed. This data will assess the efficacy of decolonization procedures on MRSA carriage rates. Patients who are not local to the clinic will not have these repeat swabs performed, but rather will be seen at the next scheduled 6 month study visit. Adherence to the study medications will be assessed at the next scheduled study visit by a patient questionnaire (refer to case report forms). Each time a patient has a positive isolate for MRSA or MSSA, this will be frozen and saved for molecular analysis to determine the most common molecular types colonizing HIV patients and to determine if patients acquire new strains or remain colonized with the same strain over time.

All study patients (both those initially found to be colonized with MRSA and those with negative colonization swabs) will be re-evaluated in six month intervals ($+/- 2$ months) until the end of the study. Patients found to be positive at these subsequent 6 month intervals, will be randomized again, treated and followed as described above. During the last study visit (at the 2-year time period), patients will have swabs, but not undergo randomization. Hence, every 6 months, patients positive during that visit for MRSA colonization will be re-randomized in a 1:1 double-blinded fashion to mupirocin (Bactroban®) nasal ointment twice daily for seven days plus hexachlorophene (pHisoHex®) washes with showering once daily for seven days or to a placebo nasal ointment (white petroleum) and a placebo body soap with no antimicrobial activity for seven days. Repeat randomization will occur every 6 months for those carrying MRSA. For example, some patients initially randomized to receive Bactroban® and pHisoHex®, may later be randomized to the placebo arm, and vice versa.

Begin at the top of diagram again every 6 months ($+/- 2$ months). If patient is found to be positive on swabs, they are re-randomized to one of the two treatment groups for every 6-month positive swab.

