Patients experiencing an infection will be offered decolonization medications based on their most recent randomization assignment; those previously randomized will be maintained in their group, while those experiencing a soft tissue infection and having a positive colonization culture for the first time will be randomized to either mupirocin (Bactroban®) nasal ointment twice daily for seven days and hexachlorophene (pHisoHex®) washes with showering once daily for seven days or to a placebo nasal ointment (white petroleum) and a placebo soap with no antimicrobial activity for seven days. Patients with a positive soft tissue culture but no positive swabs from the nares, throat, groin, axilla, or perirectal areas, will not be randomized. If the primary clinician caring for a patient who experienced a MRSA infection desires to decolonize a patient regardless of the patient's randomization group, this is permitted, but must be documented and these participants will be removed from the "placebo group" for the analysis.

All cultures (from colonization sampling, wound and blood cultures) which are positive for MRSA or MSSA at the local medical treatment facilities laboratories will be preserved by freezing the isolates at -70 degrees C; these samples will be batched (isolates will be held at the primary facility and sent on a periodic basis) and sent overnight with dry ice to the NMCSD. This site will collect the specimens and send them to the laboratory at SAMMC which will perform testing on the isolates for confirmation of MRSA, antibiotic susceptibility testing (including mupirocin), and molecular analysis (to include multilocus sequence testing, PVL PCR, and other virulence factors). Some local laboratories (e.g. NMCSD) are also performing susceptibility testing on the isolates; this information will be collected if available. SAMMC will also repeat all susceptibility testing on all isolates at their facility. All samples sent to the laboratory at SAMMC will be labeled only with a PIN number of the patient. The staff at the SAMMC laboratory will not have access to personal identifiers and will have no way of linking their results to a patient name. Results

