6.10 Termination

A subject's participation will be terminated if one of the following occurs:

- a. Subject voluntarily withdraws
- b. Subject fails to comply with study procedures
- c. Decision in the best interest of the patient
- d. Patient is no longer eligible for care at the military HIV clinics
- e. Patient becomes pregnant or decides to become pregnant during the two-year study period

- f. The patient begins employment as a healthcare worker with direct patient contact

A subject who develops a rash or significant adverse event due to study medication will be discontinued from treatment but will be encouraged to continue to undergo follow up including study visits for completing questionnaires and swabs for MRSA colonization every 6 months (+/- 2 months) until study completion; the patient will not be randomized to one of the treatment arms if he/she is found to be positive again for MRSA colonization. The subject may be withdrawn from the study if it is felt by the clinical investigators that the subject is at an undue risk from further participation.

The subject will require a termination visit if withdrawn from the study. If a subject's participation in this study is terminated, they will be offered medical standard of care and a medical evaluation, to include clinical laboratory studies as needed. The investigator will complete the Completion/Discontinuation CRF.

VII. STATISTICAL ANALYSES

There are four primary questions to be answered to address this study's primary objective. These, and an analysis designed to answer the question, follow.

- (1) What is the hexachlorophene/mupirocin treatment effect to clear MRSA colonization compared to placebo? We will also examine if these decolonization procedures are effective at reducing MRSA infections and skin/soft tissue infections compared to placebo. We propose to pool the data at 6, 12, 18, and 24 months as if they were independent and conduct a chi-square or Fisher's exact test of contingency. These analyses will be conducted for colonization and infection separately. The proposed pooling of this study design assumes that there is no persistent or repeated-treatment effect and that there is no patient-to-patient difference in susceptibility. These effects will be investigated in the following questions.

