Hence to show a statistically significant decline in colonization rates using mupirocin (Bactroban®) and hexachlorophene (pHisoHex®), up to 420 patients would be required. Given potential lost to follow-up events and that the colonization rate or clearance rates may vary, we propose to enroll 550 participants, such that 500 participants are followed throughout the study period. Given this sample size and the estimate of a 10% colonization rate over the study period, we would estimate that 50-55 participants will be randomized. Since participants with repeat colonization events may differ from those with first time MRSA colonization and may differ in response to decolonization medications, we will also examine as a secondary analysis of the primary endpoint only those with unique randomizations.

For showing a significant difference in the number of infections between the two treatment groups, assuming 38% of the no specific treatment group and 10% of the treatment group will develop infection, a sample size of 860 would be needed; of note, this is a secondary objective and not the primary basis of the sample size calculation for this study. For smaller changes in the difference in the rates between groups, larger sample size would be needed. Of note, the first rates (38% vs. 10%) were determined during an 8-10 week period and our study involves 6-month periods over a total two year period; on the other hand, this military training population studied for these estimates may have a higher rate than our HIV patients.

Infection Rate in Treated Group	Infection Rate in Placebo Group	Difference in Infection Rate Between Groups	Power	Alpha level	Total sample size for one time period	Total sample size for every 6 month evaluations
10%	38%	28%	.80	.05	860	277
10%	30%	20%	.80	.05	1440	464
10%	25%	15%	.80	.05	2260	729
5%	15%	10%	.80	.05	3200	1032

To account for the study design of patients being re-examined every 6 months over a two-year period (a total of five visits) and re-randomized at each of these intervals with new infections being counted as separate events, the sample size required was notably smaller (last column in table). The calculations accounted for a progressive decrease in colonization and infection rates over the course of the study since patients would be given decolonization medications depending on their randomization assignment.

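### The plan's only counting rule for infections treats each new infection as a separate event, but its only infection test assumes independent rows; recurrences under one assignment can push the false-positive rate above 5%.

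*Combined protocol and SAP*

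**What the plan says.** Four parts of the protocol bear on this.

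- **The test.** Section VII, question (1), proposes to "pool the data at 6, 12, 18, and 24 months as if they were independent and conduct a chi-square or Fisher's exact test" and adds: "These analyses will be conducted for colonization and infection separately". It states that the pooling assumes, among other things, that "there is no patient-to-patient difference in susceptibility".
- **The counting rule.** The Section VII sample-size text refers to the number of infections as the secondary measure. It explains the smaller sample sizes in the last column of the infection table by patients being "re-randomized at each of these intervals with new infections being counted as separate events".
- **The assignment rule.** Section 6.3: "Patients found to be positive at these subsequent 6 month intervals, will be randomized again". The arm can then change. At an infection visit the rule differs: "those previously randomized will be maintained in their group". Patients negative at a 6-month visit are not re-randomized, and nobody is re-randomized at the last visit.
- **Expected recurrence.** Section IV says of HIV-infected patients that "this group may have a propensity towards recurrent infections".

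No section defines the row of the infection table or the window in which an infection counts, and no clustered or rate model is given for infections. The analysis of unique randomizations is tied to the primary, colonization endpoint.

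**The concern.** A chi-square or Fisher test needs one independent outcome per row. Two infections in one patient within one interval share the patient and, because the arm is kept at an infection visit, share the assignment. If each becomes a row, a few patients with recurrences move both the observed rate and its apparent precision. With only 50-55 participants expected to be randomized, a handful could decide the result.

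A second route is also open. A patient negative at a 6-month visit keeps no fresh assignment. If later intervals are still counted under the old arm, several rows again hang on one randomization.

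At stake are the MRSA-infection and soft-tissue-infection comparisons: significant differences found too often when treatment has no effect, and confidence intervals that are too narrow.

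**Working it through.** **1. The plan's own figure.** Inputs (Section VII): 38% versus 10% infected, power 0.80, alpha 0.05 (taken as two-sided), 10% colonized, 1:1 allocation. With mean proportion 0.24:

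m = [1.960·√(2·0.24·0.76) + 0.842·√(0.38·0.62 + 0.10·0.90)]² / 0.28² = 35.3 per arm.

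Continuity correction: (m/4)·[1 + √(1 + 4/(m·0.28))]² = 42.2, so 43 per arm. Then 2·43/0.10 = 860, as stated. The other rows need 72, 113 and 160 per arm, giving 1440, 2260 and 3200, also as stated. This calculation is for one yes/no result per patient.

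The last column is the one-period figure divided by about 3.10 in every row (860/277 = 3.10; 3200/1032 = 3.10). The plan does not derive this factor; it attributes the reduction to repeated evaluation with separate counting of infections.

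**2. Recurrences within one interval.** Let p be the chance of any infection in an interval and r the chance that each infection is followed by another in that interval. Enter every infection as a row and compare infections with infection-free intervals. For n intervals per arm:

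- variance of the log odds assumed by the test: [(1−r)/p + 1/(1−p)]/n
- true variance: [(1+r)/p + 1/(1−p)]/n
- ratio: V = [1 + r(1−p)] / [1 − r(1−p)]

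The large-sample false-positive rate is 2·[1 − Φ(1.96/√V)]. Example: r = 0.20 and p = 0.10 give V = 1.18/0.82 = 1.44 and 1.96/1.20 = 1.63, hence 10%.

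Simulation with no treatment effect: 27 or 50 intervals per arm, p = 10%, 24% or 38%, 40,000 trials per cell for chi-square and 10,000 for Fisher. The plan gives 10% and 38% as infection rates; 24% is their midpoint. 27 is about half of 50-55; 50 is an assumed larger number that allows for repeat randomizations. Every r is an assumption, since the plan gives none.

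| r | Formula, p = 38% to 10% | Chi-square, every infection a row | Fisher, every infection a row | Chi-square, yes/no per interval |
|---|---|---|---|---|
| 5% | 5.7-6.1% | 5.9-6.5% | 1.3-4.8% | 4.9-5.6% |
| 10% | 6.6-7.3% | 6.6-7.4% | 1.7-5.3% | 4.8-5.7% |
| 20% | 8.4-10.2% | 8.2-10.1% | 3.8-7.3% | 4.9-5.8% |
| 30% | 10.4-13.7% | 10.5-13.5% | 6.9-10.3% | 4.9-5.6% |
| 50% | 15.5-22.7% | 15.5-22.4% | 13.6-19.2% | 4.9-5.7% |

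Repeat runs move the ends of these ranges by up to about one percentage point. A different model (55 patients, four freshly randomized intervals, mean 0.1-0.4 infections per interval, varying frailty) gave 6-27% for chi-square with every infection a row, and 4.8-5.3% scored yes/no.

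**3. Across intervals.** 55 patients, four intervals, one yes/no outcome each, underlying rates 10-60%, no treatment effect:

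- Fresh 1:1 assignment every interval, within-patient correlation 0-0.6: chi-square 4.7-5.5%, Fisher 3.1-4.8%.
- Only intervals that begin with a randomization: chi-square 4.8-5.2%, Fisher 3.4-4.8%.
- Old arm carried forward when not re-randomized (about 60% re-randomized per visit, assumed), correlation 0.2-0.6: chi-square 6.4-12.9%, Fisher 4.7-11.9%.

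**4. Where the window must end.** Closing it at the next randomization would be biased, because only patients still positive are re-randomized. Take the plan's 85% (placebo) and 23% (treated) still colonized, an assumed 10% chance of turning positive at each later visit, randomization at baseline, and the same 10% infection risk per 6 months in both arms. Mean window: 6·[1 + 0.15·(1 + 0.9 + 0.81)] = 8.4 months on placebo and 6·[1 + 0.77·2.71] = 18.5 months on active. A patient clear at month 6 has any infection with probability 0.1·(1−0.9²) + 0.09·(1−0.9³) + 0.81·(1−0.9⁴) = 0.322. Any infection is then 0.85·0.10 + 0.15·0.322 = 13% on placebo and 0.23·0.10 + 0.77·0.322 = 27% on active: apparent harm with equal risk.

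**The case against.** The counting phrase stands in the sample-size text and can be read as counting a later interval's infection separately from an earlier one's. The inputs there are proportions of patients infected, and a factor of 3.10 fits up to four intervals with falling rates; it needs no recurrence within an interval. Question (1) pools data by visit and never mentions event counts. On that reading there is one yes/no outcome per interval, and with fresh assignment the test holds its level.

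Most of this stands. A reader might infer that the plan's false-positive rate does exceed 5%, or that pooling repeated intervals is enough to inflate it. The documents support neither. They do not say that every infection becomes a row, and step 3 shows that fresh re-randomization keeps the level near 5% even with strong within-patient correlation. Fisher's test, which the plan also allows, shows no material inflation at 5-10% recurrence. The recurrence rates are assumed, and the plan itself warns that the 38% rate, from soldiers in training, may be higher than in HIV patients. Question (1) also states its independence assumptions openly.

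What does not fall away is that the only written counting rule is by event, the only written test needs independent rows, and nothing connects the two through a defined unit. Fresh assignment cannot help with recurrences inside one interval or with intervals that have no new assignment.

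**Conclusion.** The concern holds in conditional form. The unit and window of the infection test are undefined, and one available reading of the plan inflates the false-positive rate. If recurrences under one assignment are entered separately, chi-square rejects in about 8-23% of null trials and Fisher in about 4-19% at 20-50% within-interval recurrence. At 5-10% recurrence chi-square gives about 6-7% and Fisher roughly 5% or less. With no recurrence within an interval, and only freshly randomized intervals counted, there is no inflation. Carrying an old arm forward is a separate route, with 6.4-12.9% for chi-square under the stated assumptions.

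This concerns a secondary comparison. It does not touch the colonization test through this mechanism, since colonization is already yes/no at each visit. The correction is worth making because it is cheap and must be settled before the data are seen.

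**What to change.** In Section VII, question (1), specify for the infection analyses:

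1. **Unit and window.** Any infection, yes/no, with onset after randomization and up to the next scheduled 6-month visit; one row per randomization. The window closes at that visit in both arms, whether or not the patient is re-randomized. State how the ±2-month visit window is handled. An infection that led to a first randomization precedes it and does not count.
2. **Intervals without a new assignment.** Leave them out of the chi-square or Fisher test. If they are to be used under the earlier arm, use a model clustered by patient (GEE or robust variance).
3. **Total infections.** Analyze them only as a rate per person-time with a robust or negative-binomial standard error.
4. **Sample-size text.** Remove separate counting of infections as the basis for the test, and show how the factor of about 3.10 was obtained.

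The cost is wording only; no new data are needed. The downside is that repeat infections, and infections in later intervals without randomization, inform only the rate or clustered model.

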5.2 Subject Population

The study population will consist of those volunteers from the HIV clinics at the participating military HIV treatment centers including NMCSD, WRNMMC, SAMHS, and NMCP in their respective catchment areas. Each clinic has approximately 500 HIV-positive patients at any one time. Since all adult HIV patients are eligible who do not have allergies to the agents utilized in this study (mupirocin (Bactroban®) nasal ointment or hexachlorophene (pHisoHex®) soaps), who are not healthcare workers with direct patient contact, and who are not pregnant or breastfeeding, over 95% of clinic patients will be eligible for enrollment. A history of prior MRSA colonization and/or infection does not exclude entry into this study. The total population of the study will be 550 participants. If approximately 10-15% of participants carry the bacteria MRSA, then approximately 38 patients will receive topical antibacterial treatment and the other 38 will receive placebo. Enrollment will be on a continuous basis until 550 participants have been enrolled. The number of subjects per site will vary. The San Antonio Military Medical Center will only enroll patients that reside locally to their medical treatment facility. For the retrospective cohort, the study population will consist of all HIV patients who are 18 years or older and followed in the NMCSD HIV clinic.

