- (2) Is the treatment effect different for repeat administrations of hexachlorophene/mupirocin? The rate of MRSA positive versus negative for recolonization reoccurrence through the sequence 1 versus 2 versus 3 versus 4 treatments will be assessed by a test of trend.
- (3) Is there a persistent or repeated-treatment effect? The overall rates of MRSA recolonization at 6, 12, 18, and 24 months will be assessed by a test of trend.
- (4) Is there an individual propensity for susceptibility and what are the treatment differences between placebo and hexachlorophene/mupirocin in terms of length of time for being negative for MRSA colonization on repeated testing? A Kaplan-Meier long-rank test will be conducted on three groups: initially negative, initially positive treated with hexachlorophene/mupirocin, and initially positive treated with placebo, where survival is defined as not having acquired MRSA.

For the secondary objectives, part (a) will be assessments of the rates in which prevalence is defined as the number of patients colonized with MRSA at the beginning of

the study divided by the total population studied, and the incidence as the number of new infections per calendar time divided by the total population studied. For objective (b) examining for predictors of MRSA, we will create a multivariate logistic regression model and use a backward stepwise approach. For part (c), to evaluate if there is a significant change in the CD4 count and/or viral load pre- versus during a MRSA infection we will utilize a 1-way ANOVA. We will also compare pre-MRSA infection with after MRSA resolution as well as the counts during the infection with those after resolution. Finally, objective (d) will be a descriptive analysis of the molecular and microbiologic characteristics of the isolates. The main statistical data from the retrospective chart review study of HIV patients at NMCSD will be presented by descriptive analyses. We will compare demographics and HIV clinical data between those with and without MRSA using rank sum tests and Fisher's exact tests depending on the variable characteristics (categorical or continuous). A multivariate logistic regression model for predictors of MRSA will then be developed using a backward stepwise approach using Stata software.

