The sample size calculation for this study is based on the primary objective of the study which is to evaluate the effectiveness of decolonization procedures with application of nasal mupirocin (Bactroban®) and hexachlorophene (pHisoHex®) soaps compared to placebos with no antibacterial activity among patients found to be colonized with MRSA in the prevention of future colonization with MRSA. We will also examine the number of infections with MRSA and soft tissue infections as secondary measures of the primary objective.

The rate of MRSA colonization of the nares was 1% in a recent study involving the general US population [41]. Among HIV-infected patients this rate is higher, with one study showing a carriage rate of 27.6% [11]. However, other studies had rates of 3-9% among their HIV-infected patients [26, 27, 42]. The MRSA infection rate among HIV-infected persons is approximately 13 cases/1000 person-years in one study that examined 3,455 patients over three years with 94 MRSA infections [7]; our rate at NMCSD appears higher with 40 cases/1000 persons in the year 2005 [12].

In a study examining both MSSA and MRSA colonization rates, after treatment with mupirocin (Bactroban®), colonization was eradicated in 93%, whereas 85% who received placebo remained colonized ($P < .001$). At day 90 after study entry, 61% of the residents in the mupirocin group remained decolonized [36]. In a study by Ellis et al involving 812 soldiers over a 8-10 week period of training, of those with MRSA colonization without treatment for decolonization, 38% developed a soft tissue infection [43].

Using these data, assuming 10% of the HIV patients would be colonized, that half would be randomized to each treatment group, and that 85% in the non-treatment arm would remain colonized versus 7-39% (mean 23%) of the treated would remain colonized, we calculated the following sample sizes:

Colonization rate of the	Power	Alpha level	Sample size per group	Total sample size
--------------------------	-------	-------------	-----------------------	-------------------

Treated Group				
0.07	.80	.05	80	160
0.23	.80	.05	120	240
0.39	.80	.05	210	420

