Using these data, we proposed a sample size of 500 participants to find statistically significant results; given the long duration of follow-up and the possibility for attrition, we will enroll 550 participants accounting for 50 drop-outs.

Overall, we plan to enroll 550 participants into the study with the goal of a minimum of 50 randomizations for scientific significance. In addition, we will also examine unique randomizations, defined as a subject's initial randomization (not counting re-randomizations), as a sub-analysis of the primary endpoint. Of note since the primary endpoint includes completion of the 6 month follow-up visit after initial randomization, at least 50 subjects with these data are needed.

We plan to conduct an interim examination yearly (after at least one-half of subjects are enrolled) to determine the adequacy of the design assumptions and sample size, given that there is little literature regarding the expected colonization and infection rate in this specific (HIV) population. Also, approximately every year we will conduct an examination of the epidemiologic data regarding the prevalence and incidence of MRSA in this cohort, as well as a safety assessment.

We also calculated a sample size for the secondary objective which was to determine the predictors of MRSA colonization and infection among HIV-infected persons including examination of demographics, sexual activity, hygienic procedures, drug use, antibiotic and HAART medications, sexually transmitted diseases and HIV control. Of note, the other secondary objectives do not lend themselves to sample size calculation due to the paucity of baseline data in the literature. Predictors for MRSA were examined in three studies including Mathews et al, Lee et al, and our retrospective work [7, 12, 13]. For a power at 80%, alpha of 0.05, and examining 20 potential predictors with an R^2 of 0.10, we would need to enroll 205 patients in the study (sample power analysis, SPSS). As we examined more predictors, a larger sample size (500 to 550) is preferred.

VIII. DATA ENTRY AND ANALYSES

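### The 205-patient figure for the predictor objective is sized on a linear-regression joint test and does not carry over to the planned logistic model, which will have only about 50-55 carriers

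*Combined protocol and SAP*

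**What the plan says.** Secondary objective (b), in Section 3.2, is to determine the predictors of MRSA colonization and infection. For its analysis Section VII states: "we will create a multivariate logistic regression model and use a backward stepwise approach". No threshold for keeping or dropping a predictor is given.

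Later in Section VII the same objective receives its own sample size. The error rates are set by "For a power at 80%, alpha of 0.05", and the calculation is: "examining 20 potential predictors with an R^2 of 0.10, we would need to enroll 205 patients". The source named is an SPSS power program. No odds ratio, outcome proportion or number of events is stated. The text then prefers 500 to 550 participants on the ground that more predictors are examined.

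The expected share of carriers appears elsewhere. Section VII works with "the estimate of a 10% colonization rate over the study period" and deduces 50-55 randomized participants. Section 5.2 has a wider range: "If approximately 10-15% of participants carry the bacteria MRSA".

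**The concern.** An R-squared with a count of predictors is the input for a linear-regression power calculation. In a logistic model the information depends mainly on the number of participants with the outcome, and the 205 makes no use of that number.

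The hypothesis also differs. A power statement for R-squared across 20 predictors concerns the joint null that all 20 coefficients are zero. Objective (b) asks which individual factors predict MRSA, which is a harder question.

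At stake is a size and power attached to a named objective that its own model does not have, and a published list of risk factors selected from many candidates with few events. Section IV says that such risk-factor data may help in developing preventive strategies.

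**Working it through.** **Inputs from the documents (Section VII unless noted).** Power 0.80, alpha 0.05, 20 predictors, R² = 0.10, stated N = 205; carriers 10% (10-15% in Section 5.2); planned N 500-550; infection rates 13 and 40 per 1000 per year.

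**Inputs assumed, because the documents give none.** The meaning of R² in a logistic model; exposure prevalence of a binary predictor, 20-50%; R² of that predictor with the other covariates, 0-0.2.

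**1. Reproduce 205.** Overall F test in linear regression: u = 20, v = N − 21, f² = 0.10/0.90 = 0.111, noncentrality f²N. At N = 204 power is 0.7977. At N = 205 the noncentrality is 22.8 and power is 0.8005. The figure matches to the patient, and outcome prevalence appears nowhere in it.

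**2. Individual predictors in that same linear model.** If R² = 0.10 is split equally over 20 uncorrelated predictors, each has f² = 0.005/0.90 = 0.0056. Power for any one of them is 0.19 at N = 205, 0.38 at 500 and 0.41 at 550.

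**3. Events.** 205 × 0.10 = 20.5, or about 1.0 per candidate. 500-550 × 0.10 = 50-55, or 2.5-2.75 per candidate. At 15%, 500-550 gives 75-82, or 3.75-4.1 per candidate.

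**4. Joint test in the logistic model.** Likelihood-ratio test on 20 df, critical value 31.41, noncentrality −N ln(1 − R²_CS), where R²_CS is the Cox-Snell value. With 10% carriers the null log-likelihood per patient is 0.1 ln 0.1 + 0.9 ln 0.9 = −0.325.

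- Nagelkerke 0.10: R²_CS = 0.10 × (1 − e^(−0.650)) = 0.0478
- McFadden 0.10: R²_CS = 1 − e^(−0.0650) = 0.0629
- Cox-Snell: 0.10

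| Meaning of R² = 0.10 | Noncentrality at 205 | Power at 205 | Power at 500 | Power at 550 |
|---|---|---|---|---|
| Nagelkerke | 10.0 | 0.40 | 0.87 | 0.91 |
| McFadden | 13.3 | 0.55 | 0.96 | 0.98 |
| Cox-Snell | 21.6 | 0.82 | >0.99 | >0.99 |

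Under Nagelkerke, 80% power needs N = 428. With 15% carriers, power at 205 becomes 0.49, 0.70 and 0.82.

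The values at 205 are approximate, because large-sample theory is poor at one event per parameter. In simulation at 205, type I error was 0.096 instead of 0.05; power was 0.46 under Nagelkerke and 0.85 under Cox-Snell.

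**5. Detectable odds ratio for one binary predictor.** Let P be the overall carrier proportion, B the exposure prevalence, p₀ and p₁ the risks without and with exposure, and ρ² the R² with other covariates:

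N = [1.96√(P(1−P)/B) + 0.842√(p₀(1−p₀) + p₁(1−p₁)(1−B)/B)]² / [(p₁−p₀)²(1−B)(1−ρ²)]

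Example: P = 0.10, B = 0.30, ρ² = 0, odds ratio 2.27 gives p₀ = 0.0757 and p₁ = 0.1568. Then N = (1.0735 + 0.5177)²/(0.0811² × 0.70) = 550.

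Over B = 20, 30, 40 and 50% and ρ² = 0 and 0.2, the odds ratio detectable with 80% power is:

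| Carriers | N = 205 | N = 500 | N = 550 |
|---|---|---|---|
| 10% | 3.83-5.48 | 2.33-2.79 | 2.24-2.67 |
| 15% | 3.07-3.82 | 2.03-2.42 | 1.96-2.33 |

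**6. Infection as outcome.** Two years at 13-40 per 1000 per year, with complete follow-up, gives 500 × 2 × 0.013 = 13 to 550 × 2 × 0.040 = 44 cases. That is fewer than the carriers.

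**7. Multiplicity.** Twenty independent tests at 0.05 give 1 − 0.95²⁰ = 64% chance of at least one false positive. At 0.10 the chance is 1 − 0.90²⁰ = 88%.

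**The case against.** The strongest reply is that 205 is not what the trial enrols. Section VII moves straight on to 500-550, the total is fixed at 550, and the trial is sized on its primary objective. A reader might infer from the mismatch that the predictor analysis lacks 80% power. The documents do not support that for the joint test: step 4 gives at least 0.87 at 500-550 under all three usual definitions, and even at 205 the Cox-Snell reading exceeds 80%, although with inflated type I error. A latent-scale R² of 0.10 is less favourable (simulated power 0.32 at 205 and 0.66 at 500), but the plan does not say which definition it means.

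A reader might also infer an arithmetic error. There is none: 205 is correct for the test that it sizes.

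A third tempting inference is that backward selection itself creates false predictors. The check does not show this. In 300 simulated null data sets per sample size, a full 20-predictor logistic model without selection had at least one p<0.05 in 66% (N = 205) and 67% (N = 550); backward selection kept at least one in 63% at both sizes. These rates are ordinary multiplicity, as in step 7, and the 0.05 threshold is itself an assumption.

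These replies stand and limit the point. They do not supply a link between the R² calculation and the logistic model. Nor do they answer the question of individual predictors. The plan's reason for preferring 500-550, that more predictors are examined, lowers the events per candidate further.

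**Conclusion.** The point holds as a method mismatch on a secondary objective. The 205 patients and their 80% power belong to a joint linear-model test and carry over neither to the planned logistic model nor to the identification of individual predictors. At 205 the joint logistic test would have power of about 0.40 to 0.82 with 10% carriers, depending on the undefined R².

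At the planned size the joint test is not the weakness. The weakness is 50-55 carriers (75-82 at 15%) for 20 or more candidates. For one binary predictor, 500-550 patients can detect with 80% power an odds ratio of about 2.2-2.8 at 10% carriers, or about 2.0-2.4 at 15%. These ranges rest on the assumed exposure prevalences and covariate R² in step 5. The infection model will be weaker. The primary analysis and randomization are unaffected.

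**What to change.** In Section VII, withdraw the 205 figure with its 80% power. In its place, state the expected number of carriers and the odds ratio that 500-550 patients can detect for one predictor, with the assumed exposure prevalence, carrier proportion and correlation with other covariates. Add that the infection outcome will have fewer events.

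Replace unrestricted backward stepwise selection with either a short predictor set named in advance or a penalised logistic model fitted to all candidates. The reasons are the few events per candidate and the multiplicity of 20 or more tests.

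The cost is a text change. The stated precision becomes less favourable, and the analysis reports fewer predictors or shrunken odds ratios. Enrolment does not change.
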